Study Design

Non-random participatory action research consisting of discussion groups and facilitated meetings

Study Procedures

Over the course of the grant year, each step of the project is divided into three month portions. The first quarter will be dedicated to recruiting and forming a

cohort of TGNC individuals, drawn mostly from the LGBT Center’s extensive contact lists and centrality within the TGNC population. We plan on recruiting 20 individuals to ensure we meet the minimum retention of 12 subjects throughout the study needed for qualitative saturation (Guest, Bunce, and Johnson 2006), and individuals between 14-18 years of age will be able to participate with guardian permission. Interested individuals will fill out applications to identify their interests and ability to commit to the project and will allow us to create a cohort that reflects the diversity of the TGNC community in Cuyahoga County, including gender identity, types of gender-affirmative care required (including whether or not someone is considering, in the process of, or completed physical transition), racial and ethnic identity, age (over 14), and socio-economic class. Upon accepting the invitation to participate, each member of the cohort will complete a pretest that will elicit data on their experiences in the healthcare system, their knowledge of basic and transgender-specific medical terminology, their familiarity with healthcare providers in Cuyahoga County, and the likelihood of seeking care under a number of conditions (acute, chronic, moderate, severe). We expect this to take one month. The following two months will consist of meeting as a cohort twice a month. The first two meetings will be dedicated to understanding the group’s collective experiences with health care, what they would like to see change, and what strategies can be used to accomplish those ends. We recognize that TGNC people come from a variety of backgrounds and each will bring their own strengths, networks, and perspectives to the table which will allow us to make full use of the indigenous expertise of the group. In consultation with the Nursing School of CWRU, we will develop a health literacy training that meets the expressed needs of the cohort and [name] will present it during the 3rd meeting. The goal here is not to provide all possible health education but rather to arm the cohort with the skills and language to empower them to act as advocates on their own behalf when navigating the healthcare system. The final meeting (the 4th) in this first quarter will be with a trained facilitator ([name]) who will, under the direction of the TGNC cohort, plan a series of three interactive dialogues between the TGNC cohort and the healthcare providers. By meeting with the TGNC cohort first, without the healthcare providers, the TGNC cohort will have the opportunity to ensure the dialogues are designed to meet their objectives. Individual healthcare practitioners and medical staff will be recruited during the first quarter from the aforementioned clinics. We will recruit at least twelve providers and twelve staff members, who will attend one meeting each. All of the clinics we have documented support from and those we are in current dialogue with have previously reached out to the LGBT Center for training in this area, and CMEs may be available through MetroHealth. In the second quarter, we will

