
conduct a pretest that will collect data on attitudes towards TGNC individuals, TGNC-specific healthcare concerns, depth and breadth of referral networks for TGNC providers. Once the healthcare provider group is solidified, the LGBT Center will host three evening meetings (once per month) with the trained facilitator wherein TGNC individuals lead a conversation about what they see as barriers to their care, how they would like to be treated, and what they want healthcare providers to know about them as people. The first two meetings will be with healthcare practitioners and the final meeting will be medical staff so that the meetings can be more specific and without the interference of power dynamics within the provider groups. Healthcare providers and staff will only attend one meeting each. During this second quarter, the TGNC cohort will continue to meet on its own once a month to debrief from meetings, respond to what they have learned so far, and possibly refine the strategies for future meetings with healthcare providers as the series goes forward. At the end of the three months of dialogue, each participant, from both the TGNC cohort and healthcare provider, will be given a post-test to measure changes in attitude, practice, and knowledge. Participants will also have the opportunity to engage in a reflective interview. The third quarter will diverge onto two different paths: the LGBT Center project coordinator will continue to engage with the cohort as they shift into the role of peer educators and advocates with other members of the TGNC community that interact at the LGBT Center. [name] will conduct follow-up interviews with any TGNC cohort member that notifies the researchers that they have sought medical care and with any healthcare provider that notifies the researchers that they have had a clinical interaction with a TGNC individual. We will not be seeking any protected medical information or the identity of patients, in the case of healthcare providers, but rather a discussion of the ease or difficulty in communication, levels of comfort, and comparison with other interactions in general. Throughout the process, both [name] and the LGBT Center coordinator will be engaged in participant observation (Bernard, 2002; Denzin & Lincoln, 1994) and keep detailed field notes on all the meetings. All participant observation will take place during the scheduled cohort meetings which will not be recorded except through note-taking. All interviews will be transcribed unless the participant chooses not to be recorded; interviews and field notes will be coded with a priori codes (Bernard & Ryan, 2010) derived from the literature on reducing health disparities and TGNC-specific health care by a research assistant. Participants may choose to participate in an optional reflective interview where they are asked to reflect on the appropriateness and effectiveness of the project in meeting their expectations. Pre- and post-tests will be analyzed to determine the success of facilitated dialogue in improving confidence and knowledge by both the TGNC

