
cohort and the healthcare providers, and depending on sample size, we will determine if there are any statistically significant changes. This analysis and write up will encompass the last quarter of the project.

Study Timeline

	Pre-Screening	Meetings 1-18	Facilitated meetings	Optional interviews
Estimated time requirement of visit for TGNC cohort	Fill out on own	1.5 hours		1.5 hours
Estimated time requirement of visit for medical providers			2 meetings, 1.5 hours each	1.5 hours
Estimated time requirement of visit for medical staff			1 meeting, 1.5 hours	1.5 hours

Devices

If the research involves device(s), describe your plans to use the device(s).

N/A

ClinicalTrials.gov Information

Case Western Reserve University Protocol Record IRB-2018-2194, TRANSLATE: Transgender and Gender Nonconforming Individuals' Access to Healthcare, has been reviewed and will be made public on ClinicalTrials.gov.

List of Data to be Collected

Note: If using REDCap, all selected identifiers below must be indicated as PHI.

1. *Indicate what identifiers you will collect*
 - Name
 - Address (e.g., Zip code, other geographical designation, etc.)
 - Dates related to an individual (e.g., Date of admission, birth, surgery, etc.)
 - Telephone number
 - Fax number
 - Email address
 - Social security number
 - Medical record number
 - Health plan beneficiary number
 - Account number
 - Certificate/license number
 - Any vehicle or other device serial
 - Device identifiers or serial numbers
 - Web URL
 - Internet protocol (IP) address
 - Finger or voice prints

- Photographic images
- Other: Any characteristic that would uniquely identify the individual

2. List all other data to be collected for the research study (e.g. laboratory values, physician notes, length of stay, etc.)

Data Analysis Plan

Pre and post tests will analyze knowledge gained. Qualitative data analysis with atlas.TI will be performed on field notes based on meeting observations and any optional interviews completed.

Confidentiality of Data

1. To maintain the confidentiality of the data:
 - I will use a unique study identifier (not derived from the participants personal identifiers) to code individuals' data and I will store this ID log separate from study data.
 - Other (please explain) Upon completion of the study, identifiers will be destroyed, leaving only the unique coded identifier in fieldnotes and transcripts. Voice recordings will be destroyed as soon as interviews are transcribed.

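### Provider and staff pre/post change has no untreated comparison, so it can show change during the programme but not that the dialogue caused it

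*Combined protocol and SAP*

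**What the plan says.** Study Design describes the project as "Non-random participatory action research consisting of discussion groups and facilitated meetings".

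Study Procedures sets out the provider and staff arm:

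- **Numbers and exposure.** "We will recruit at least twelve providers and twelve staff members, who will attend one meeting each". The exposure is repeated later in the section: "Healthcare providers and staff will only attend one meeting each".
- **Pretest.** In the second quarter the team will "conduct a pretest that will collect data on attitudes towards TGNC individuals, TGNC-specific healthcare concerns, depth and breadth of referral networks for TGNC providers".
- **Dialogues.** "Once the healthcare provider group is solidified, the LGBT Center will host three evening meetings (once per month) with the trained facilitator". On who attends which: "The first two meetings will be with healthcare practitioners and the final meeting will be medical staff".
- **Post-test.** One post-test is given to every participant when the three months of dialogue are over.
- **Use of the data.** "Pre- and post-tests will be analyzed to determine the success of facilitated dialogue in improving confidence and knowledge", for both the TGNC cohort and the providers. Significance is to be assessed if the sample is large enough.

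The Data Analysis Plan adds only that the tests will look at knowledge gained. No control group, waiting group, repeat baseline or test between meetings is described.

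The Study Timeline table has a different exposure for medical providers: "2 meetings, 1.5 hours each".

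**The concern.** Every provider and staff member has attended a dialogue before the only post-test. The pre/post difference therefore combines any effect of the dialogue with the effect of seeing the items twice, of being enrolled and observed, and of anything else learned over about three months. Outside learning is plausible here, because Study Procedures says the participating clinics had already approached the LGBT Center for training on this subject. Nothing in the plan limits the causal reading or mentions these alternatives.

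At stake is the answer to the second research question, whether the dialogues lead to more provider confidence. The consent section also suggests that a successful result could be repeated elsewhere. As planned, a rise in scores would be read as the dialogue working when the data cannot tell that from a rise that would have happened anyway.

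The schedule already contains an unused source of information. On the Study Procedures text, later groups wait untreated between the pretest and their own meeting, and nobody measures them at the end of that wait.

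**Working it through.** The plan gives no SD, effect size, alpha or power for providers or staff, so there is no stated figure to reproduce.

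**Inputs from the documents.** 12 providers and 12 staff; three meetings a month apart, two for practitioners and one for staff; one pretest and one post-test.

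**Assumptions.** Practitioners split 6/6 over their two meetings, giving 6/6/12; normal change scores; two-sided 5% level; all effects in SDs of the change score; drift of 0.2 to 0.8 SD, for illustration only.

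**Step 1: the schedule** (approximate; exact dates are not given)

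| Group | n | Extra wait before own dialogue | Dialogue to post-test |
|---|---|---|---|
| Practitioners, meeting 1 | 6 | none | about 2 months |
| Practitioners, meeting 2 | 6 | about 1 month | about 1 month |
| Staff, meeting 3 | 12 | about 2 months | near zero |

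**Step 2: how often drift alone would look like success.** With a true dialogue effect of zero and drift d, the paired t statistic is noncentral t with n − 1 degrees of freedom and noncentrality d√n. For n = 12 and d = 0.5 the noncentrality is 0.5 × √12 = 1.73, against a critical value of 2.201.

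| Drift (SD) | n = 12 | n = 24 pooled |
|---|---|---|
| 0 | 5% | 5% |
| 0.2 | 10% | 16% |
| 0.3 | 16% | 29% |
| 0.5 | 35% | 65% |
| 0.8 | 71% | 96% |

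A larger sample makes the false attribution more likely, not less.

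**Step 3: what one repeat form on arrival would show.** The 95% half-width of the mean waiting-interval change is t(n − 1, 0.975)/√n.

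- 12 staff: 2.201/√12 = 0.64 SD.
- 6 second-meeting practitioners: 2.571/√6 = 1.05 SD.
- Both pooled, n = 18: 2.110/√18 = 0.50 SD. This mixes two roles and two lengths of wait, so it should not be the reported figure.

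**Step 4: subtracting the waiting change.** The net quantity is (post − mid) − (mid − pre) = post − 2·mid + pre. With equal variances σ² and equal correlations ρ across the three tests, its variance is 6σ²(1 − ρ). One change score has variance 2σ²(1 − ρ). The ratio is 3, so each half-width grows by √3 = 1.73: about 1.10 SD for 12 staff, 1.82 SD for 6 practitioners and 0.86 SD for 18 pooled.

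**Step 5: comparing practitioners at meetings 1 and 2 directly.** With a further test before meeting 2, 6 v 6 gives a half-width of 2.228 × √(1/6 + 1/6) = 1.29 SD. Power is 12% for a 0.5 SD effect, and 80% power needs 1.80 SD.

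**The case against.** The strongest reply is that this is a small one-year participatory project that openly calls itself non-random, and that the absence of a control is a design preference. The only sample-size rationale is qualitative saturation for the TGNC cohort. Significance testing is conditional, and the tests sit beside field notes and interviews. Much of this stands. A reader might infer that an uncontrolled design is itself the fault; the documents do not support that, since such a design is acceptable for a project of this kind. What remains is the causal use of the result. The interviews are optional or triggered by self-report, so they add context but no comparison.

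A second reply is that the untreated wait is inferred. The text does not state that everyone is tested at once before the first meeting. The order of the sentences puts the pretest before the meetings, but testing each group close to its own date is not excluded. The practitioner wait also depends on one meeting each, which the Study Timeline table contradicts. If each provider attended both meetings, only the staff wait would be left.

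A third reply concerns the remedy. A reader might infer that the stagger supplies a ready waiting-list control, so that the result could be stated as change beyond the waiting change. It does not:

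- Staff wait about two months but are post-tested soon after their meeting, so the two intervals are not alike.
- The first retest falls in the wait and the second after the dialogue, so practice effects need not cancel.
- First-meeting practitioners have no comparable wait.
- Meeting 3 is all staff, so contrasts between staff and practitioners are confounded with role.
- The TGNC cohort may adjust its approach between meetings, so meetings 1 and 2 may differ.

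These limits stand, and they restrict the repeat form to a descriptive role.

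**Conclusion.** The concern holds in a limited form. As written, the plan would use provider and staff pre/post change to judge the dialogue although nothing separates its effect from drift, retesting or other learning. The size of the risk depends on drift that the documents do not give: for 12 people, the chance of a significant change with no dialogue effect runs from 10% at 0.2 SD to 71% at 0.8 SD.

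Two stronger readings should be avoided. A reader might infer that scores would probably rise whatever the dialogue did; no figure in the documents supports that, and it is only plausible. A reader might also infer that the stagger can yield a net effect of the dialogue; Steps 4 and 5 show that such an estimate would be too imprecise, and the interval mismatch would bias it. The waiting change is useful as a descriptive estimate of untreated change, where at present there is none. The figures rest on the 6/6/12 split, a pretest given before the first meeting, and one meeting per provider.

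The wording problem is not confined to providers and staff. The same sentence covers the TGNC cohort, which also has no comparison.

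**What to change.** 1. **Repeat the existing form.** Give the same pretest again on arrival to second-meeting practitioners and third-meeting staff. Report the waiting-interval change beside the change from that test to the post-test, separately by role, with interval lengths and 95% confidence intervals. Label it descriptive, and do not make the difference between the two the headline result.
2. **Reword the conclusion.** In Study Procedures and the Data Analysis Plan, describe pre/post results for all groups, including the TGNC cohort, as change during the programme rather than as the success of the dialogue.
3. **Reconcile the exposure.** Study Procedures and the Study Timeline table disagree on how many meetings each provider attends. Resolve this before relying on a practitioner waiting interval. State at the same time when the pretest is given relative to the first meeting.

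The cost is one extra short form for about 18 people on the assumed split, on evenings already planned, and one more exposure to the test items. No extra participants or meetings are needed. The rewording costs nothing and is the minimum even if the repeat form is not adopted.

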2014; The Fenway Institute, 2017). Studies on reducing LGBTQ+ health disparities have included restructuring electronic health records and data collection methods (Cahill et al., 2014; Callahan, Hazarian, Yarborough, & Sánchez, 2014), addressing myths and establishing best practices (McNamara & Ng, 2016), and macro-analysis of intersectionality between institutions providing transgender healthcare (Stroumsa, 2014). More in line with our proposal are studies that focus on direct, personal intervention with healthcare providers (Lelutiu-Weinberger et al., 2016), advocacy led by community members (Cartwright, Desiderio, Green, Persson, & Tescher, 2012), and based directly on self-assessed patient needs (Alpert, CichoskiKelly, & Fox, 2017; Bevan, 2013). The annual Philadelphia Trans Wellness Conference includes a professional track for medical providers on issues such as primary care management and gender affirming medical procedures, exemplifying both a community need for improved quality of care and interest within in the medical field (Mazzoni Center, 2018).

Inclusion and Exclusion Criteria

Directions: Describe how individuals will be screened for eligibility. Using the tables below, describe the inclusion and exclusion criteria that will define who will be included and excluded in your final study sample.

	Inclusion
1.	Age range: 14 years old and up
2.	Self-identifies as transgender or gender non-conforming
3.	
4.	

	Exclusion
1.	Under the age of 14
2.	Non-English speaking
3.	
4.	

Number of Research Participants

We will enroll 20 participants in the transgender/gender non-conforming cohort, 12 medical providers, and 12 clinic staff.

Vulnerable Populations

1. Indicate specifically if you will include each of the following special populations by checking the appropriate box:

- Adults unable to consent**
- Minors (infants, children, teenagers)**
 - Wards of the state
 - Foster Children
- Pregnant Women**
- Neonates**
- Neonates of Uncertain Viability**
- Employees of CWRU or UHHS**

- Prisoners**
- Illiterate Individuals**
- Non-English Speaking**
- University Students**
- None**

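### Significance testing depends on an unstated sample size and looks for any change, with no main score per group and no paired estimate with an interval

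*Combined protocol and SAP*

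**What the plan says.** The inferential plan is the closing part of Study Procedures. It reads "Pre- and post-tests will be analyzed to determine the success of facilitated dialogue in improving confidence and knowledge by both the TGNC", and the sentence then completes the pair of groups as the TGNC cohort and the healthcare providers. It ends with the rule that "depending on sample size, we will determine if there are any statistically significant changes". The Data Analysis Plan section adds only "Pre and post tests will analyze knowledge gained" on the quantitative side.

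The content of the tests is described elsewhere in Study Procedures. The TGNC instrument is described thus: "pretest that will elicit data on their experiences in the healthcare system, their knowledge of basic and transgender-specific medical terminology, their familiarity with healthcare providers", together with their likelihood of seeking care under several conditions. The provider-side pretest covers "attitudes towards TGNC individuals, TGNC-specific healthcare concerns, depth and breadth of referral networks for TGNC providers". At the end of the dialogues each participant "will be given a post-test to measure changes in attitude, practice, and knowledge".

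On numbers, the section on research participants says "We will enroll 20 participants in the transgender/gender non-conforming cohort, 12 medical providers, and 12 clinic staff". Study Procedures explains the 20 as a way to keep at least 12, for qualitative saturation.

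**The concern.** Two features of the rule leave the quantitative result open until the data are in.

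- **The condition has no threshold.** Nothing says how many pairs are enough, or whether the decision is made once or separately by group and outcome.
- **The target is any change.** No score is put first, and the three descriptions of what is analysed do not agree. Confidence, which aims 1 and 2 of the Research Question ask about, is in the analysis sentence but not among the listed pretest or post-test domains.

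The protocol uses these tests to judge whether facilitated dialogue succeeded, and says elsewhere that a successful programme could be repeated in other places. A chance positive could feed that claim. Conversely, in groups this small a bare non-significant result tells the reader almost nothing, and no interval is promised that would show how much change remains possible.

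**Working it through.** **1. Is there a plan figure to reproduce?** No statistical one. The only sample-size reasoning is 20 recruited to retain 12. These agree if 40% are lost, 20 × (1 − 0.40) = 12, but the 40% is inferred, not stated. Alpha, power, effect size and SD are not given. Below, alpha is assumed to be 0.05 two-sided per test, and effects are in SDs of the within-person change.

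**2. Outcomes side by side.**

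| Place | Outcomes | Groups named |
|---|---|---|
| Research Question, aims 1 and 2 | confidence | TGNC; providers |
| Study Procedures, analysis sentence | confidence, knowledge | TGNC; providers |
| Data Analysis Plan | knowledge | none |
| Study Procedures, post-test | attitude, practice, knowledge | TGNC; providers |
| Study Procedures, TGNC pretest | experiences, terminology knowledge, familiarity with providers, care-seeking (4) | TGNC |
| Study Procedures, provider pretest | attitudes, TGNC-specific concerns, referral networks (3) | provider side |

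Staff are enrolled separately (12), but the analysis sentence does not name them.

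**3. Chance of at least one false positive if nothing changes, independent tests.** The formula is 1 − 0.95^m.

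- m = 4 (two outcomes × two groups, as the analysis sentence names them): 1 − 0.95^4 = 18.5%
- m = 7 (4 TGNC + 3 for providers and staff as one group): 30.2%
- m = 9 (three post-test domains × three groups): 37.0%
- m = 10 (4 TGNC + 3 provider + 3 staff): 40.1%
- m = 14, the first count to pass one half: 51.2%

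**4. Allowing for correlation.** Ten paired t-tests were simulated under no change (40,000 runs; n = 20, 12, 12; groups independent; equal correlation between domains within person).

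| Correlation | At least one p < 0.05 |
|---|---|
| 0.3 | 39% |
| 0.5 | 36% |
| 0.7 | 32% |
| 0.9 | 25% |

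**5. Precision of one paired comparison.** Detectable change is from noncentral-t power at 80%. The 95% CI half-width is t(0.975, n−1)/√n.

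| n | Detectable change (SD) | CI half-width (SD) | Power for 0.5 SD |
|---|---|---|---|
| 12 | 0.89 | 0.64 | 35% |
| 20 | 0.66 | 0.47 | 56% |
| 24 (providers and staff pooled) | 0.60 | 0.42 | 65% |

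An interval can be computed at each of these sizes, so a sample-size condition is not needed for reporting one.

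**6. After naming one score per group.** Three scores each tested at 0.05 would still carry 1 − 0.95^3 = 14.3%. At 0.05/3 each the figure is 4.9%, and the detectable change rises to 1.08 SD at n = 12 and 0.78 SD at n = 20.

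**The case against.** The full analysis sentence is narrower than its last clause. It names two outcomes in two groups, and the Data Analysis Plan names knowledge alone. The count of ten is built here from pretest topics, and treats staff as a separately tested group, which the protocol does not say. This stands, and it is why the size is given as a range starting at 18.5%. It does not close the point, because the last clause is not tied to those two outcomes and the other descriptions differ.

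Achieved numbers are uncertain: 20 are recruited to keep 12, and provider and staff numbers are minimums in Study Procedures. Caution about testing is therefore reasonable, and deciding on sample size alone does not inflate type I error. This also stands. What is missing is the threshold and a default report that does not depend on it.

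The study is mainly qualitative and sized for saturation, so the quantitative part is secondary. That limits the weight of the point but does not remove it, since the pre/post tests are what the protocol uses to judge success.

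A reader might infer several stronger claims that the documents do not support:

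- That a chance positive is more likely than not. This needs at least 14 independent tests. Item-level testing is neither planned nor excluded, and nothing sets out ten domains in each of three groups.
- That testing is decided after seeing outcome data. The condition is on sample size only.
- That any single significant test defines success, or that a non-significant result will be read as no change. Neither rule is written.

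**Conclusion.** The concern holds in a limited form. The plan makes testing conditional on a size it does not state, searches for any significant change, names no main score per group, describes its outcomes inconsistently, and promises no paired estimate with an interval. The false-positive risk is substantial but not shown to be likely: 18.5% for four tests, up to about 40% for ten, and about 25% to 39% for ten with within-person correlation from 0.9 down to 0.3. These figures rest on an assumed two-sided alpha of 0.05 per test and on counts of comparisons that the protocol does not fix. The unrestricted search drives the risk. The absent threshold adds only the possibility of selective testing by group or outcome. Separately, groups of 12 to 20 can detect only changes of about 0.89 to 0.66 SD with 80% power, so estimates with intervals would be far more informative than a list of p-values.

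**What to change.** Replace the conditional sentence in Study Procedures, and align the Data Analysis Plan with it, as follows:

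1. For each group, name one score before the first pretest, measured in both pretest and post-test. Analyse it as the mean within-person change with 95% CI, whatever sample size is reached.
2. If that score is confidence, as aims 1 and 2 suggest, add confidence items to both questionnaires, because the described tests do not list it. Otherwise name a listed domain such as knowledge, and make sure it is measured both before and after in that group. A missing baseline cannot be recovered once pretesting has begun.
3. State whether providers and staff form one group or two.
4. Report all other domains, and the doctor versus nurse-practitioner difference, as descriptive estimates with CI and no significance claim.
5. If the named scores will also be tested, state the alpha and whether it is shared across groups (see step 6 of the working).

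The cost is a few sentences and possibly a few questionnaire items. The downside is that fewer results can be called significant. This is a cheap improvement.
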